8.2. Efficacy Assessments and Procedures

Efficacy assessments are not evaluated in this trial.

8.3. Safety Assessments and Procedures

The following safety and tolerability measures will be implemented throughout the trial at the time points listed in [Table 1](#) to [Table 5](#):

- inquiries about AEs (Section 8.4)
- physical examinations and physical measurement findings (Section 8.3.1)
- vital signs measurements (Section 8.3.2)
- ECG findings (Section 8.3.3)
- clinical laboratory test results (Section 8.3.4)
- neurological and clinical symptom assessments (█████████████████████, ██████████, ██████████, and ██████████) (Section 8.3.5)
- local injection site tolerability and pain assessments (Section 8.3.6)

- injection site pus-containing lesion (abscess, infection, or inflammation), ulceration, necrosis, or atrophy monitoring (Section 8.3.7)
- PDSS monitoring (Section 8.3.8)
- medication error and special situations related to the IMP (Section 8.3.9)
- overall tolerability (Section 8.3.10)
- pregnancy and postpartum information (Section 8.5)
- clinical product complaints (Section 8.6)
- concomitant medication usage (Section 6.8)

In the case of a suspected PDSS event, an adjudication committee will be summoned to review all cases of suspected PDSS. Further details on the adjudication committee are provided in Section 10.2.

8.3.1. Physical Examinations

Physical examinations and physical measurements (height, weight, and calculation of BMI) will be performed at the time points detailed in Table 1 to Table 5.

A complete physical examination will be conducted at the screening and EOT visits. Physical examinations will include, at a minimum, assessments of general appearance, head, ears, eyes, nose, throat/neck [HEENT], lymph nodes, respiratory system, cardiovascular system, gastrointestinal system, musculoskeletal system including extremities, neurological system, and dermatological system. An abbreviated physical examination (general appearance, HEENT, lung, heart, skin, and extremities) will be conducted at the other time points and will include a brief neurological examination that includes assessment of mental status and examination of a subset of cranial nerves controlling vision and motor examination of a subset of larger muscle groups, including an assessment of muscle tone, reflexes, gait, and involuntary movements.

Any physical examination finding that is assessed by the Investigator as a clinically significant change (worsening) compared with a baseline value will be recorded as an AE, recorded on the CRF, and monitored as described in Section 8.4.4.

8.3.2. Vital Signs

Vital signs, including body temperature, respiratory rate, supine or semi-supine pulse rate and blood pressure (systolic and diastolic), and their orthostatic changes, will be measured at the time points detailed in Table 1 to Table 5.

Orthostatic blood pressure and heart rate will be determined with measurements obtained after the participant has been supine or semi-supine for at least five minutes and repeated after the participant has been standing for 3 minutes.

All vital sign results outside of the reference range will be interpreted by the Investigator as belonging to 1 of the following categories:

- abnormal but not clinically significant
- abnormal and clinically significant

When applicable, vital signs will be measured after ECGs but before scheduled blood draws.

Before pulse, blood pressure, and respiratory rate are measured, the participants must be in a supine or semi-supine position and resting for at least 5 minutes. The same position and arm (opposite arm from the cannula site) should be used each time vital signs are measured for a given participant, when possible. For any abnormal vital signs finding, the measurement should be repeated as soon as possible.

Any vital sign result that is assessed by the Investigator as clinically significant will be recorded on the source documentation, transcribed to the CRF as an AE, and monitored as described in Section 8.4.4. In addition, potentially clinically significant values may be predefined by the Sponsor for selected vital signs and, if so, this will be documented in the Statistical Analysis Plan or other relevant documents (eg, medical monitoring plan).

8.3.3. *Electrocardiograms*

ECGs will be measured at the time points detailed in [Table 1](#) to [Table 5](#).

All ECG results outside of the reference range will be interpreted by a qualified physician as belonging to 1 of the following categories:

- abnormal but not clinically significant
- abnormal and clinically significant

When applicable, ECGs will be performed before vital signs measurements and scheduled blood draws. Before each ECG is performed, the participants must be in a supine or semi-supine position and resting for at least 5 minutes. At screening only, the ECG will be performed in triplicate at 5-minute intervals.

A qualified physician or designee at the clinical investigational site will be responsible for interpreting the ECGs. Any ECG finding that is assessed by the Investigator as a clinically significant change (worsening) compared with a baseline value will be considered as an AE, recorded on the source documentation, transcribed onto the CRF, and monitored as described in Section 8.4.4.

8.3.4. *Clinical Laboratory Tests*

8.3.4.1. *Chemistry, Hematology, Coagulation, and Urinalysis*

Clinical laboratory tests (chemistry, hematology, coagulation, and urinalysis) will be performed following an overnight fast of at least eight hours at the time points detailed in [Table 1](#) to [Table 5](#). Non-fasting blood collection is permitted as needed, per the Investigator's assessment of AEs.

Clinical laboratory tests on samples collected during day 1 and day 3 may be performed via both local and central laboratories, as described below. Non-fasting blood collection is permitted as needed, per Investigator assessment of AEs.

Specific laboratory tests to be performed are listed in Section 13.2. At each urinalysis collection, females will be asked if they are currently menstruating, and this information will be recorded in the source documents and CRF.

All clinical laboratory test results outside of the reference range will be interpreted by the Investigator as belonging to one of the following categories:

- abnormal but not clinically significant
- abnormal and clinically significant (AE, as described in Section 8.4.1)

A laboratory test result that is assessed by the Investigator as clinically significant will be recorded as an AE and monitored as described in Section 8.4.4. An event may include a laboratory or diagnostic test abnormality (once confirmed by repeated testing) that results in the withdrawal of the participant from the trial, the temporary or permanent withdrawal of IMP or medical treatment, or further diagnostic work-up. (Note: Abnormal laboratory or diagnostic test results at the screening visit that preclude a participant from entering the trial or receiving IMP are not considered AEs).

In addition, potentially clinically significant values will be predefined by the Sponsor for selected laboratory test variables and detailed in the Statistical Analysis Plan or other relevant documents (eg, medical monitoring plan or laboratory analysis plan).

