- i. Presence of excessive pigment, bruises, scars, or tattoos around the potential injection area.
- j. Presence of any local skin infection, rash, or anything else that limits injection administration and assessment of injection site.
- k. Donated or received any blood or blood products (eg, white blood cells, platelets) within 60 days prior to screening, or has donated blood or blood products on 2 or more occasions within 6 months prior to IMP administration, or has donated plasma within 7 days prior to screening, or has planned donations during the 56 days or 5 half-lives following the last dose administration, whichever is longer. The minimum reference volume of whole blood lost or donated is 500 mL.
- l. Vulnerable participants (eg, prisoners or institutionalized individuals), participants who pose a significant risk of suicide attempt in the Investigator's judgment based on

medical history, answered “yes” to Suicidal Ideation items 4 or 5 on the [REDACTED] for “current” or “within 3 months prior to screening,” or had a suicide attempt or hospitalization due to suicide risk within 12 months prior to screening.

- m. 12-lead electrocardiogram (ECG) demonstrating intraventricular conduction delays (QRS interval \geq 110 msec or PR interval \geq 200 msec) and have a mean of triplicate QTcF values $>$ 450 msec for males and $>$ 470 msec for females at screening or other clinically significant ECG findings that would interfere with trial participation as judged by the Investigator.
- n. Personal or family history of arrhythmia, sudden unexplained death at a young age (before 40 years) in a first-degree relative, long QT syndrome, personal history of syncope, or history of uncontrolled high blood pressure. Participants with history of high blood pressure who no longer require treatment or participants who are treated with antihypertensive medications and whose blood pressure is currently well-controlled, may be enrolled.
- o. Supine or semi-supine blood pressure outside the range of 90 to 140 mm Hg for systolic or 50 to 90 mm Hg for diastolic (following at least a 5-minute rest). Note: If either value is out of range, blood pressure measurements may be repeated in the supine or semi-supine position at intervals of 5 to 10 minutes up to 2 times. If the systolic or diastolic measurement continues to exceed the stated limits, the participant will be excluded.

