5.5. Prior Therapy and Medication

Any prior therapy, medication, or procedure a patient has had within 30 days before study drug administration will be recorded on the CRF. Trade name or INN, indication, and dosage will be recorded. The sponsor will encode all therapy and medication according to the World Health Organization (WHO) drug dictionary (WHO Drug).

The incidence of prior therapies and medications will be summarized using descriptive statistics by therapeutic class and preferred term. Patients are counted only once in each therapeutic class category, and only once in each preferred term category.

5.6. *Electrocardiography*

Electrocardiogram findings (normal, abnormal not clinically significant, abnormal clinically significant, and missing) in screening period, AP WO period (day 3) and on day R1 in period 3 will be summarized using descriptive statistics.

5.7. *Childbearing Potential and Methods of Contraception*

For female patients, information related to childbearing potential, and menopause will be collected at the time points specified in Table 1 to Table 5 of the trial protocol. Data will be listed.

For female and male patients, methods of contraception will be collected at the screening period. Data will be listed.

5.8. *Trial Protocol Deviations*

Data from patients with any important protocol deviations during the trial will be summarized for overall and each category using descriptive statistics. All protocol deviations will be listed.

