7.10. Electrocardiography

ECGs will be measured at the time points detailed in Table 1 to Table 5 of the trial protocol.

Shifts (normal and abnormal) from baseline to each visit that it is measured will be summarized using patient counts. For overall finding, the summary will use the worst post-baseline finding for the patient (the abnormal finding if there are both normal and abnormal findings). Summary statistics for ECG variables will be presented at baseline and each visit. Actual values and changes from baseline to each visit will be summarized using descriptive statistics. The incidence of potentially clinically significant abnormal values for ECG variables will be summarized using descriptive statistics with the criteria specified below.

- QT interval corrected using Fridericia's formula (QTcF) values >450 msec, or >480 msec, or >500 msec.
- QTcF change from baseline values >30 , or >60 .
- PR change from baseline $\geq 25\%$ and value >200 .
- QRS change from baseline $\geq 25\%$ and value >110 .
- Heart rate value <60 bpm or >100 bpm.

[figure not shown]
The number (%) of participants with QTcF change from baseline values >30 , or >60 , will be also presented separately for Period 3 (day R1 to day R29)

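### The ECG shift table in SAP 7.10 uses only normal/abnormal, so it cannot show how many participants moved to a clinically significant ECG, although that grade is already collected

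*Protocol*

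**What the plan says.** **Grading at the site.** Protocol 8.3.3 states: "All ECG results outside of the reference range will be interpreted by a qualified physician as belonging to 1 of the following categories". The two categories are "abnormal but not clinically significant" and "abnormal and clinically significant". With normal, that makes three recorded levels.

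**Baseline-type summary.** SAP 5.6 keeps all three levels plus missing: "Electrocardiogram findings (normal, abnormal not clinically significant, abnormal clinically significant, and missing) in screening period", and also on washout day 3 and on day R1. It is a summary at each of those times, not a shift.

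**Post-baseline analysis.** SAP 7.10 has two levels: "Shifts (normal and abnormal) from baseline to each visit that it is measured will be summarized using patient counts". For the overall row it takes the worst post-baseline finding, defined as "the abnormal finding if there are both normal and abnormal findings". The same section separately summarises ECG values, changes from baseline, and numeric criteria for QTcF, PR, QRS and heart rate.

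**Adverse event route.** Protocol 8.3.3 also says that an ECG finding which the Investigator assesses as a "clinically significant change (worsening) compared with a baseline value will be considered as an AE". Protocol 8.4.1.1 repeats the rule.

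**The concern.** The plan collects a three-level reading, reports it before sc dosing, and then drops one level in the table meant to show change. Participants with an NCS baseline ECG can enter the trial: apart from its interval limits, exclusion criterion m removes only "other clinically significant ECG findings that would interfere with trial participation as judged by the Investigator". If such a participant later has a CS ECG, the shift table shows abnormal to abnormal. For a participant with a normal baseline, a trivial abnormality and a clinically significant one fall in the same cell.

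At stake is how well this table serves its purpose. ECG findings in the 24 hours after ZYPREXA im are a listed exploratory measure in Protocol 3.4 and SAP 1.4. Protocol 3.4 also lists them for day 1 to R84. A reader of the study report would expect the ECG shift table to show whether any formulation was followed by clinically significant ECG readings. As specified, it cannot.

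**Working it through.** The plan gives no figure to reproduce, so the check sets the passages side by side and counts cells.

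**1. Where the three-level grade is reported.** Protocol Tables 1 to 5 schedule ECGs at screening and on days 3, 4, 5, 7, 12, R1, R2, R8, R15, R29 and R84. SAP 5.6 reports the grade at screening, day 3 and R1. The R1 ECG is pre-dose for the sc product but follows ZYPREXA im on day 4, so it is one three-level summary after the im dose. No visible text plans a three-level summary for days 4 and 5, or for any visit after sc dosing.

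**2. How nine cells become four.** Rows are baseline and columns are post-baseline. Each entry is the SAP 7.10 cell into which the combination falls.

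| Baseline | Normal | NCS | CS |
|---|---|---|---|
| Normal | normal to normal | normal to abnormal | normal to abnormal |
| NCS | abnormal to normal | abnormal to abnormal | abnormal to abnormal |
| CS | abnormal to normal | abnormal to abnormal | abnormal to abnormal |

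Count: 1 + 2 + 2 + 4 = 9. Abnormal to abnormal holds four different combinations, including one worsening (NCS to CS) and one improvement (CS to NCS), and all four read as no change. Of the three worsening combinations, two are pooled together and the third sits in the unchanged cell.

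**3. Can the CS count be recovered from the table?** The number with a CS reading is normal-to-CS + NCS-to-CS + CS-to-CS. None of these is a separate cell in the two-level table, and its abnormal margin gives only NCS + CS. The answer is no.

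**4. The worst-finding rule.** A participant with NCS at R8 and CS at R15 is carried as abnormal. So is one with NCS at both visits. The rule ranks abnormal over normal and has nothing to say within abnormal.

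**5. Illustration only.** The documents give no ECG rates, so every input here is assumed: n = 20 per cohort; baseline NCS share b = 0.10, 0.30 or 0.50, with the rest normal; P(CS given NCS) = 0.10; P(CS given normal) = 0.05; P(NCS given normal) = 0.25. Only b is varied.

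| b | NCS to CS: 20 × b × 0.10 | Normal to abnormal: 20 × (1 − b) × 0.30 | of which CS: 20 × (1 − b) × 0.05 |
|---|---|---|---|
| 0.10 | 0.2 | 5.4 | 0.9 |
| 0.30 | 0.6 | 4.2 | 0.7 |
| 0.50 | 1.0 | 3.0 | 0.5 |

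Under these inputs, at most about one participant per cohort is shown as unchanged when the reading went to CS. One participant is 1/20 = 5% of a cohort. This shows the order of size under the stated inputs. It is not an estimate for this trial.

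**The case against.** The strongest reply is that nothing clinically important goes missing. A reader might infer from the two-level table that a clinically significant ECG worsening would go unreported. The documents do not support that. Protocol 8.3.3 and 8.4.1.1 make such a worsening an adverse event. SAP 7.2 tabulates adverse events by system organ class, preferred term and CTCAE grade, separately for periods 1 + 2, period 3 and follow-up, and SAP 7.1 adds cohort and treatment. A rhythm or T-wave change judged a clinically significant worsening would appear there.

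A reader might also infer that a participant with an NCS baseline can register no worsening at all. That is not so. SAP 7.10 itself summarises QTcF thresholds and changes, PR and QRS changes, heart rate limits, and changes from baseline at each visit. Only the categorical shift is blind.

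Nor does the SAP contradict the protocol's analysis text. Protocol 9.5 promises descriptive summaries and a comparison with predefined criteria; it prescribes no levels for an ECG shift table. The measure is exploratory. The visible SAP 1.4 list for overall trial safety does not repeat ECG findings (part of that list is redacted), and the visible ECG measure for the sc formulations is numeric QTcF change.

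All of this stands and limits the weight of the point. It does not make the table adequate. Adverse event tables count by preferred term, not by ECG reading against baseline status and visit. They also rest on the Investigator's judgement of change, whereas each ECG is read by a qualified physician or designee. The numeric criteria do not use that reading. One could argue that the two-level wording is shorthand for a fuller table shell, but the worst-finding rule is written out with the same two levels.

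**Conclusion.** The point holds as a limited one. SAP 7.10 discards a distinction that Protocol 8.3.3 requires and SAP 5.6 already reports. Its shift table and worst-finding row therefore cannot show how many participants developed a CS ECG after dosing, and they show NCS to CS as unchanged.

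This rests on the text alone and needs no assumption about rates. The number of participants affected cannot be derived from the documents. The loss is of information in one descriptive table supporting an exploratory safety measure. Capture of clinically significant ECG events, the primary PK analysis and the sample size are unaffected. It is worth changing because the improvement is almost free, not because a result would otherwise be wrong.

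**What to change.** In SAP 7.10, specify the shift table over the SAP 5.6 categories: normal, abnormal NCS, abnormal CS, and missing. Define the worst post-baseline finding as CS over NCS over normal. This gives NCS to CS and normal to CS their own cells.

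The cost is a small wording change covering the shift levels and the worst-finding rule, and a shell of nine cells plus missing in place of four. The grade is already collected, so no CRF, visit or sample size change follows. SAP 2.5.2 allows SAP amendments to be approved before database lock.

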8.3.4.1.1. Laboratory Values Meeting Hy's Law Criteria

All occurrences of possible drug-induced liver injury that meet Hy's law criteria, defined as all of the criteria listed below, must be reported by the Investigator to the Sponsor as an SAE:

- ALT or AST increase of $>3 \times$ ULN
- total bilirubin increase of $>2 \times$ ULN
- absence of initial findings of cholestasis (ie, no substantial increase of alkaline phosphatase)

8.3.4.2. Other Laboratory Tests

8.3.4.2.1. Screening Laboratory Tests

At screening, participants will be tested for hepatitis B surface antigen, hepatitis C virus antibody, human immunodeficiency virus (HIV)-1 antibodies, and HIV-2 antibodies.

8.3.4.2.2. Follicle-stimulating Hormone

At screening, women who have been amenorrheic for at least 1 year without an alternative medical cause will have a serum follicle-stimulating hormone (FSH) assessment to confirm postmenopausal status (an increased concentration of FSH of >35 IU/L in women not using hormonal contraception or hormonal replacement therapy [HRT]).

For pregnancy testing, see Section 13.1.3.

8.3.4.2.3. Human Chorionic Gonadotrophin Test

HCG tests in serum or urine will be performed for all women at the time points specified in Table 1 to Table 5.

A serum pregnancy test will be administered for all women, regardless of childbearing potential at screening, on day 1, day 12, and R84 (EOT). Serum or urine dipstick pregnancy tests will be

performed for all women of childbearing potential (WOCBP) on day 3. Negative pregnancy results on day 1, day 3, day 12 (which will be performed locally and centrally), and, if Period 2 is extended, day R1 are mandatory prior to IMP dosing. Additional pregnancy tests may be performed, as determined necessary by the Investigator or required by local regulation, to establish the absence of pregnancy at any time during the participant's participation in the trial.

Any participant who becomes pregnant during the trial will be withdrawn. Procedures for reporting the pregnancy are provided in Section 8.5.

8.3.4.2.4. Alcohol and Drug Screen

A serum drug and alcohol screen will be performed at screening. The serum drug screen is to detect the presence of drugs of abuse, including amphetamines, barbiturates, benzodiazepines, cocaine, opiates, and tetrahydrocannabinol.

An in-house urine dipstick screen for prohibited drugs and breathalyzer for alcohol will be performed on day 1, day 3, day 12 (to be conducted at the discretion of the Investigator), day R1 (if Period 2 is extended), day R15, and day R84 (EOT). Alcohol and drug screens may be performed at additional time points at the discretion of the Investigator.

Any positive result during trial conduct will be managed according to the Investigator's review and judgment, in consultation with the Sponsor's medical representative.

8.3.5. Neurological and Clinical Symptoms Measures

The following neurological and clinical symptoms measures (_____ , _____ , _____ , and _____) will be administered by a trained rater at the time points specified in Table 1 to Table 5.

8.3.5.1.

A series of seven horizontal black bars of varying lengths, decreasing in length from left to right. The bars are positioned in a row, with the first bar being the longest and the seventh bar being the shortest.

8.3.5.2.

A series of five horizontal black bars of increasing length, starting from a short bar on the left and ending with a very long bar on the right. The bars are evenly spaced and have a consistent thickness.

8.3.5.3.

8.3.5.4.

8.3.5.5.

8.3.5.6.

